7.0 Data Management and Information Security

7.1 Data Management

Data management will be almost exclusively web-based, with paper-based surveys available as needed for mailing. The UW CCC will support an https-secured web page that

provides a centralized location for public information about the project for potential subjects, investigators, and institutional agencies. The web page will contain a link to the project portal (<https://uwdcc.org/portal/impepe>). Study personnel will log on to the private portal on the study web page with individual single sign-on (SSO) authentication usernames and passwords to securely perform study data management activities. An overview of the DCC responsibilities and data management system is presented below.

Study Integration: The UW DCC team has extensive experience developing Application Programming Interfaces (APIs), which allow multiple software programs to seamlessly interact and communicate with one another in a simple and intuitive interface. The web portal API will serve as the wrapper for all data management tools and software utilized in the IMPEDE Trial, including: study ID assignment, screening, centralized image storage (if needed), prospective data collection forms and surveys, and study operations reporting. Screening and eligibility will be determined centrally through the portal and all subjects screened under the trial protocol will be assigned a sequentially generated study participant ID. The DCC will maintain a REDCap database to centrally and securely store patient information, with distinct data access groups for clinical recruitment sites.

Electronic Data Capture: The UW DCC supports its own installation of REDCap, which is software specifically designed for electronic data capture that we have used successfully in several multi-site clinical trials. REDCap features include differentiated user roles and privileges, password and user authentication security, electronic signatures, SSL encryption, and comprehensive auditing to record and monitor access and data changes (<http://www.project-redcap.org/software.php>). REDCap will serve as the architectural backbone for all data captured prospectively in this study, with all data linked by study subject ID. The web-based data management portal allows for three participant contact methods: research coordinator data entry; electronic survey; or computer-assisted telephone interviewing (CATI). All survey modalities are customized to incorporate project logos and information to increase participant recognition and response rate. Furthermore, surveys may be distributed on any time schedule (e.g., monthly for pain and disability), and in any designated survey format.

All study questionnaires completed on paper will be reviewed by study staff for accuracy and completeness.

7.1.2 Data Quality Monitoring

The CCC and DCC will review participant enrollment, reasons for exclusion, participant demographics, and follow-up rates by site in order to assess proximity to enrollment targets, site performance, and protocol adherence.

The DCC will perform in-line quality assurance checks by using field masking, range checks, and real-time warning messages. Missing data reporting and other customized reports will be developed by the DCC in collaboration with the CCC and recruitment team in order to facilitate efficient work-flow and high-quality data capture. A subset of key personnel from the DCC and CCC will serve as an operations committee and review quality control reports on a weekly or biweekly basis, though quality control reports will be made available on a daily basis. CRF-specific follow-up rates will be tabulated on a nightly basis and reviewed during the weekly check-in meeting with each clinical recruitment site. Nightly, the DCC will generate graphs that monitor CRF-specific follow-up rates over time as well as data quality trigger rates over time to prospectively monitor potential issues that may develop gradually or acutely over time. A data query resolution dashboard will be available to each site on a continuous basis. In similar studies, we have found that establishing a fixed-day for a monthly review of all unresolved queries is an adequate balance of time to resolution and alert fatigue.

On a nightly basis, the DCC will also generate a comprehensive data quality report to flag unusual data and will be made broadly available to the study team. Research staff at the recruitment sites will be asked to review each outstanding query and respond with “confirmed” or “corrected” and may provide a comment beside each query to note relevant details. Each query will be closed by the DCC protocol operations specialist.

7.2 Information Security

All participant data collected on paper will be stored in locked file cabinets located in the site research offices.

All data entered onto UWMC laptop/desktop computers sites will be secured via our Information Security infrastructure. Information Security at UWMC is multi-layered and includes physical security measures, network security measures, managed servers, and desktop/laptop computers with authentication and authorization controls. All systems are designed and implemented to properly secure restricted or confidential information, including PHI, from inadvertent or unauthorized disclosure. All policies and procedures adhere to federal, state, and health system requirements. Servers, desktops, and laptops are under active management by an Integrated Technology Services Group (ITSG) at each participating site. In addition to maintaining anti-virus and firewall installations, the ITSG audits patch status of systems connected to the network and installs any missing updates or patches found. Servers have defined change control periods for operating system maintenance but are patched or updated outside the schedule as necessary to address threats. Anti-virus software is configured to update daily. The host-based firewalls restrict inbound connections to only the subnets where department workforce resides or that are needed for firewall administration. The firewall rule set on the dedicated server is further restricted to the network subnets. A specific Windows domain account is required to access computers. Domain passwords must be at least 8 characters in length, conform to complexity rules, and be changed at least every 120 days. Database systems and security policies are established and overseen by administrative staff members who do not require research funding.

REDCap:

All data, including PHI, names, and contact information will be entered onto a HIPAA and 21 CFR Part 11- compliant database. Participant PHI, including names, contact information, health information, will be entered onto this database. Only study staff will have access to the database and each study staff member will be given separate access only after completing study-required trainings.

8.0 Statistical Analysis Plan and Stopping Rules

The IMPEDE Trial is based on the Practice-Based conceptual model for comparative effectiveness;¹⁶² “there is a comprehensive set of patient, treatment, and outcome variables, and [that by] analyzing them we identify treatments associated with better outcomes for specific types of patients”. The strategy for utilizing this model is that a lack of evidence related to the effectiveness of interventions to prevent recurrent diverticulitis is limiting treatment options and leading to excessive use of preventative colon resections. Also, structural barriers (e.g., affordability of Medi For All) may result in differential acceptance of medical management among historically disadvantaged groups.

8.1 Allocation and Randomization

The Data Coordinating Center (DCC) will generate and maintain randomization assignments. Randomization assignments (2:1 randomization; N=50 to USDA Med-style Food Pattern (Medi For All): N=25 to standardized guidance on fiber intake) will be generated separately by site using block randomization randomly permuted block sizes for each site. Research coordinators will randomize eligible patients using a web-based portal that provides the next available assignment once an eligible patient consents for study participation. Study participants will be unblinded to the assigned intervention group (USDA Med-style Food Pattern or standardized guidance on fiber intake), but CERTAIN investigator team and research staff involved in data collection will be blinded to intervention status.

8.2 Study Feasibilities Measures

We will assess willingness to randomize as the number of eligible patients that randomized divided by the number of eligible patients (Aim 1). We will provide descriptive statistical summaries of time to complete survey materials, time interacting with the USDA Med-style Food Pattern platform, and changes in estimated weekly meal expenses. These data will be used to inform the future large-scale trial including the number of study sites, recruitment rate/study duration and amount of coordinator effort. The rate of willingness to randomize is unknown but as long as it is at least 20% our study will be successful. We would also want at least 50% of those willing to randomize to be willing to give a blood sample and at least half of those to give stool.

8.3 Treatment Fidelity and Adherence:

The Fred Hutch FFQ is a standard method of dietary intake assessment that has been used in several large-scale cohort studies including the Women’s Health initiative.^{153, 154} The degree of adherence with the USDA Healthy Med-style Food Pattern (Aim 1) will be ascertained by assigning point scores based on the estimated daily amounts of the recommended food groups and subgroups habitually consumed. Full points will be awarded to diets that meet all the

recommendations and partial points to diets that do not. Given that the USDA Healthy Med-style Food Pattern provides recommended amounts for relevant food groups, the adherence score will be based on food consumption data normalized per 100 kcal, much along the lines of the Healthy Eating Index (HEI). The HEI is a 100-point score that measures adherence to the DGA and is the standard measure of diet quality in the US. This approach represents an advance over the 14-item food frequency MEDAS score, which ranks adherence to the Med-style diet pattern using 3 cutpoints: ≤ 7 , 8–9, or ≥ 10 (maximal adherence).¹⁴⁵ The data derived will help us understand the central tendency and variability in Med-style food pattern scores which is critical for determining the sample size of a future trial. Degree of adherence to the different aspects of the medical management regimen will also be used to define per-protocol analysis and be considered as potential mediators and/or effect modifiers in explanatory regression models

8.4 Signal Assessment for Biomarkers:

We will use a linear mixed effects regression model to compare IL-6, IL-10, IL-1 β , and fecal calprotectin measures at baseline, 6, and 12 months after randomization between the two groups. We focus our statistical analysis on IL-6 for which there are preliminary data specific to diverticulitis. The linear mixed effects model will be structured as a longitudinal analysis of covariance, allowing for both cross-sectional and longitudinal comparisons of serum biomarkers between intervention groups. From the model, we will estimate the mean difference and 95% confidence interval in time-averaged IL-6 by averaging the time-specific intervention group differences. The longitudinal analysis of covariance model will adjust for intervention (USDA Med-style pattern versus standardized guidance on fiber intake), recruitment site, and baseline IL-6 as fixed effects: $IL6(t) \sim \beta_0 + \beta_1 \cdot Intervention + \beta_2 \cdot Site + \beta_3 \cdot IL6(t=0)$, for $t = 6$ and 12 months. Follow-up time-point specific differences in mean IL-6 between intervention groups will be estimated by a statistical interaction term between time and intervention status in a second model. Finally, experience in other ongoing trials has shown that serum biomarkers are often positively skewed. We will therefore log-transform IL-6 measurements (and all skewed serum biomarkers) throughout all statistical analyses, and exponentiate model coefficients (as appropriate) for interpretation. Sex and gender (if different from sex assigned at birth) will be considered as exploratory variables in assessing the relationship of the diet-behavioral intervention and the primary and secondary outcomes. Analyses of IL-10, IL-1 β , and fecal calprotectin and patient-reported outcomes will mirror the analyses of IL-6, with the primary goal of estimating plausible intervention effect sizes and standard deviations with the goal of informing a larger phase 3 clinical trial. Formal statistical testing will not be conducted and therefore no multiple testing correction will be employed for analyzing multiple serum biomarkers. Sex as a biological variable will be included in an exploratory analysis of all biomarker models. The study of serum and stool biomarkers will also inform the feasibility of performing a biomarker sub-aim within a future phase 3 trial.

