3.0 Study Aims and Methods

3.1 Study Aims

Aim 1. Conduct a randomized trial (n=75) of the USDA Healthy Med-style Food Pattern intervention versus standardized guidance on fiber intake for patients with diverticulitis to determine feasibility of a larger-scale effectiveness trial focused on long-term clinical outcomes (recurrence and complications). We will examine willingness to randomize and assess adherence to USDA Healthy Med-style Food Pattern.

Aim 2. Explore plasma inflammatory markers in a subset of participants (n=40) (IL-6, IL-1, IL-1 β) and fecal calprotectin as short-term, intermediate inflammatory biomarkers of response to treatment and collect samples for future biomarker study.

The hypotheses underlying the IMPEDE trial include 1) A large-scale trial of the USDA Med-style Food Pattern will be feasible (high rate of patient willingness to be randomized, high rate of adherence to the intervention, improvement in Med-style food pattern scores assessed by a well-characterized food frequency questionnaire (FFQ) [measure of extent of use of the Mediterranean diet], acceptability of study survey burden and follow-up). 2) A USDA Med-style Food Pattern reduces serum and fecal biomarkers of inflammation more than standardized

recommendation to encourage a high-fiber diet. Based on prior studies, we expect reductions in these biomarkers will correlate to lower rates of recurrent diverticulitis.

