6.0 Outcome Assessments

6.1 Primary and Secondary Outcomes

Patient Reported Outcomes (PROs) will be assessed for adults using both generic and disease-specific surveys utilizing the QoL instruments in Table 2.

Table 2. Primary and secondary outcomes and intervention related process measures.

| Primary or Secondary | Name of Outcome | Specific Measure to Be Used | Time Point |
|----------------------|---|--|------------------------|
| Primary | Willingness to enroll | Enrolled/approached | Baseline |
| Primary | Adherence to USDA Med-Style Food Pattern | USDA Med-style Pattern score calculated from the NASR FFQ. ¹⁶¹ | Baseline, 6, 12 months |
| Primary | Participant retention | Proportion enrolled and retained at 3, 6, 9 and 12 months | 3, 6, 9 and 12 months |
| Primary | Interaction with on-line program | Number of times accessed | Bi-weekly |
| Primary | Engagement with nutrition services | Number of sessions with dietician | Quarterly |
| Secondary | Plasma, IL-6, IL-10, IL-1 β , fecal calprotectin | Concentration | Baseline, 6, 12 months |
| Secondary | Diverticulitis events | Self-reported (presumed), subset of those resulting in healthcare utilization (e.g., hospitalization, surgery). | Quarterly |
| Secondary | NSQIP-defined complications, a subset of which are serious adverse events to be reported to ISM | Standardized assessment-serious events defined as death, cardiac arrest, myocardial infarction, pneumonia, progressive renal insufficiency, acute renal failure, pulmonary embolism, deep vein thrombosis, return to operating room, serious site infections | Quarterly |
| Secondary | DVQOL ⁶⁵ | A 17-item questionnaire that assesses four domains: symptoms, concerns, emotions, and behavior changes related to diverticulitis. | Baseline, 6, 12 months |
| Secondary | GIQLI ¹⁵⁹ | A 36-item questionnaire that assesses five domains: gastrointestinal symptoms, physical function, emotional well-being, social well-being, and perception of medical treatment measured by a single item question. | Baseline, 6, 12 months |

| | | | |
|-----------|--------------------------------|--|------------------------|
| Secondary | IPAQ Short Form ¹⁶⁹ | A validated 7-item questionnaire: moderate and vigorous physical activity, walking, and sitting in the past 7 days | Baseline, 6, 12 months |
| Secondary | Time in healthcare | Days missed from work/school, ED/hospital encounters, diverticulitis-related diagnostic/therapeutic interventions | 3, 6, 9 and 12 months |

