8.7 Sample Size and Statistical Power

Using 2:1 randomization, we will enroll 50 patients into a USDA Med-style Food Pattern and 25 patients to receive standardized guidance on fiber intake. The analytic aim of this study is to inform potential effect sizes and variance estimates toward the ultimate goal of conducting a definitive phase 3 randomized trial. While 1:1 randomization is more statistically efficient when group variances in outcome are similar, we plan to enroll more participants into the USDA Med-style food pattern intervention to strengthen the precision of estimates of adherence and patient-reported response. Since statistical testing will not be formally conducted, statistical power was not a primary motivation for sizing for this pilot study.¹⁶⁶ However, enrollment of 50 study participants in the USDA Med-style Food Pattern intervention allows a 95% one-sided confidence interval for the intervention adherence rate to exclude rates less than 0.70 if the observed adherence rate is 0.80 or higher in this pilot study.

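### Section 8.2 calls the study successful on 20% willingness alone, although the protocol's own definition of feasibility also requires adherence and acceptable follow-up

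*Combined protocol and SAP*

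**What the plan says.** Section 8.2 describes the willingness rate as not yet known and states of it: "as long as it is at least 20% our study will be successful". The next sentence adds specimen targets as wishes. For blood it reads: "We would also want at least 50% of those willing to randomize to be willing to give a blood sample". For stool, the hope is for samples from half or more of the blood donors. Neither is made a condition of success, and neither concerns adherence or retention.

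Section 3.1 describes feasibility more broadly. Hypothesis 1 lists "high rate of patient willingness to be randomized, high rate of adherence to the intervention, improvement in Med-style food pattern scores", followed by acceptable survey burden and follow-up. None of these carries a number there.

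Table 2 in section 6.1 names five primary outcomes: willingness to enroll, adherence to the food pattern, participant retention ("Proportion enrolled and retained at 3, 6, 9 and 12 months"), interaction with the online program, and engagement with nutrition services. Only willingness has a success threshold anywhere in the document, and no retention target is given.

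Section 8.7 justifies the 50 participants in the Med-style arm by an adherence calculation. A one-sided 95% interval would "exclude rates less than 0.70 if the observed adherence rate is 0.80 or higher". It also says that the 2:1 allocation gives up some efficiency to estimate adherence more precisely.

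**The concern.** The pilot exists to show whether a larger trial of this diet intervention can be run. That question has at least three parts: whether patients will enter, whether they will follow the diet, and whether they will stay. The success sentence answers only the first, but its subject is the study and not recruitment. Followed literally, it lets a pilot with poor adherence and poor retention be reported as a success in support of a larger trial, against the protocol's own definition of feasibility.

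Adherence and retention also need to be read together. Section 5.5 lists pursuit of a conflicting diet among the reasons for withdrawal, and under section 5.5.1 participants who ask to be withdrawn have no further scheduled follow-up. Adherence among those who remain can therefore look good while retention is poor.

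**Working it through.** **Inputs.** Willingness threshold 20% (section 8.2); 75 randomized, 50 of them to the Med-style arm (sections 8.1 and 8.7); one-sided 95% confidence and a 0.70 reference for adherence (section 8.7). The 20% threshold is stated without derivation, so there is nothing to reproduce for it.

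**Step 1: reproduce the figure in section 8.7.** The one-sided 95% Wald lower limit is p − 1.645 × √(p(1 − p)/n). With p = 40/50 = 0.80 and n = 50:

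0.80 − 1.645 × √(0.80 × 0.20/50) = 0.80 − 1.645 × 0.0566 = 0.707.

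This excludes rates below 0.70, so the statement is reproduced. It depends on the method: at 40/50 the Wilson limit is 0.693 and the exact (Clopper-Pearson) limit 0.684. Both need 41/50 to clear 0.70.

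**Step 2: apply the success sentence to a poor pilot.** The adherence and retention counts below are illustrative, not predictions.

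| Component | Illustrative result | Effect on the section 8.2 label |
|---|---|---|
| Willingness | 75/375 = 20% (75/0.20 = 375 eligible at most) | Decides it: met |
| Adherence, Med-style arm | 20/50 = 40% | None |
| Retention at 12 months | 30/75 = 40% | None |

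The lower limit for adherence is 0.40 − 1.645 × √(0.40 × 0.60/50) = 0.40 − 1.645 × 0.0693 = 0.286, or about 0.29. This is far below the 0.70 used to size the arm, and the study is still labelled successful.

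**Step 3: the same contrast in probability.** If true adherence were 0.60, the exact binomial chance of observing at least 40/50 is 0.2%. The condition described in section 8.7 would be missed 99.8% of the time, while the section 8.2 label would not move.

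**Step 4: would a hard adherence bound be a sound replacement?** Exact chance of passing, with all 50 participants measured:

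| True adherence | At least 40/50 | At least 41/50 |
|---|---|---|
| 0.60 | 0.2% | 0.1% |
| 0.70 | 7.9% | 4.0% |
| 0.80 | 58.4% | 44.4% |
| 0.85 | 88.0% | 79.1% |
| 0.90 | 99.1% | 97.6% |

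At true adherence of 0.80, a pass-or-fail bound would be close to a coin toss. Missing questionnaires make it harder: 32/40 is also 80% observed, but its Wald limit is 0.80 − 1.645 × √(0.16/40) = 0.696, below 0.70.

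**Step 5: can adherence and willingness be computed as the plan stands?** Section 8.3 defines a graded score with full and partial points. Section 8.5 refers to an adherent-or-not indicator, but no cutoff is given. Willingness is randomized eligible patients over all eligible patients in section 8.2, but "Enrolled/approached" in Table 2. Both must be settled before any joint conclusion can be drawn.

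**The case against.** The strongest reply is that the sentence is loosely worded and meant only for recruitment. It sits in the paragraph that defines willingness, it is followed by specimen targets, and adherence has its own section (8.3). The document contains no go/no-go rule for the larger trial. The pilot's stated purpose is to supply descriptive estimates, and the other primary outcomes will be reported whatever the label says. This limits the consequence: adherence and retention cannot change the word successful, but they can still inform planning. It does not remove the problem, because the sentence speaks of the study and nothing qualifies it. If recruitment was meant, the correction simply says so.

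A reader might infer two stronger points, and the documents support neither.

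- **That the verdict is reached before any adherence or retention data exist.** Platform use is recorded bi-weekly, retention from month 3 and the food frequency questionnaire at month 6, and section 8.8 provides for reports at 50%, 75% and full enrollment. Unless enrollment is very fast, some of these data will exist when recruitment closes. The accurate point is that the label does not depend on them.
- **That the rule contradicts the 0.70 bound.** Section 8.7 offers that figure as a statement of precision, after saying that no formal testing will be done. The success sentence ignores it but does not conflict with it.

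It is also fair to say that turning 0.70 into a hard criterion would impose a test for which the pilot was not sized. Step 4 bears this out.

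**Conclusion.** The concern holds in this form: section 8.2 makes 20% willingness sufficient to call the study successful, while hypothesis 1 and Table 2 treat adherence and follow-up or retention as parts of feasibility too. The direct conflict is with hypothesis 1 for adherence. Retention is not named there; it enters through acceptable follow-up and as a primary outcome in Table 2.

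The size of the gap is that a pilot with 40% adherence (lower limit about 0.29) and 40% retention keeps the same label as one with excellent results on both. This rests on reading the sentence as written and on the illustrative counts. It also assumes that some cutoff will define an adherent participant. The documents give no expected dropout or retention target, so no retention threshold can be derived from them.

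**What to change.** Replace the success sentence in section 8.2 with: *willingness of at least 20% will be taken as evidence that recruitment is feasible*. Then state that overall feasibility will be concluded only from three results together:

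- willingness;
- adherence in the Med-style arm, as an estimate with its one-sided 95% lower limit, reported against the 0.70 reference in section 8.7;
- retention.

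These should be judged against targets that the sponsor sets before outcome data are reviewed. If only willingness is met, the conclusion is that recruitment is feasible, and no more. The lower limit need not be a pass-or-fail test.

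To make this usable, specify:

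1. the cutoff that turns the graded food-pattern score into adherent or not;
2. the interval method, since 40/50 clears 0.70 under Wald but not under Wilson or the exact method;
3. how participants with missing food frequency questionnaires count toward adherence;
4. one willingness denominator, eligible or approached, used in both section 8.2 and Table 2.

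The change is to wording and definitions; no data collection is added. The costs are that the sponsor must commit to targets in advance and that success becomes harder to claim.
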